Cover page:

Official title of the study:

The Effect of Complementary Medicine (CAM) Treatments on Common Symptoms in Hospitalized Patients

Date: June 15th, 2016

Background

Cholecystectomy due to gallstones is one of the most common operations in general surgery. Nowadays, this type of surgery is usually done electively in the laparoscopic method (LC – Laparoscopic Cholecystectomy), in Israel and worldwide. In recent years, ERAS (enhanced recovery after surgery), an international association of experts in the fields of surgery, anesthesia, and other allied health professions, has led a process of formulating guidelines, based on research evidence, in order to improve perioperative care. This trend reflects an interventionist approach and a global perspective on the public health level in the context of surgery which, among others, highlights the need to address peri-operative symptoms.

The state of preoperative anxiety may affect the course of surgery usage of anesthetics⁴, and the recovery period that follows in different aspects, such as pain^{5,6}, wound healing⁷, nausea and vomiting⁸, duration of hospitalization and recovery⁹, immune system status.¹⁰ Preoperative anxiety is usually evaluated using the VAS-A (Visual Analog Scale for Anxiety) questionnaire, which is based on the patient's own reporting and is a reliable, simple and quick method, particularly when the time available for interaction with the subject is limited, as is the case in the HRA (Holding Room Area), a waiting room in which patients stay for 15-50 minutes before surgery.¹¹⁻¹⁴

Between 11% and 80% of adult patients undergoing surgery, report experiencing significant (moderate-to-high) preoperative anxiety.^{15,16} A controlled, randomized clinical trial on 360 surgical patients showed that 70% of the subjects experienced moderate-to-high levels of anxiety approximately one hour before the surgery, despite being treated with the standard-of-care (SoC), which involves administering anxiolytics prior to the surgery at the discretion of the anesthesiologist.¹⁷

Anxiolytics are often administered before surgery, either orally or by intravenous injection. Several studies have proven the efficacy of using anxiolytics as part of premedication before surgery, including midazolam¹⁸, gabapentin¹⁹, diazepam²⁰ and oxazepam.²¹ However, data obtained from several other studies cast doubt on their effectiveness.^{22,23} Several studies have demonstrated the effectiveness of different complementary medicine treatments, including reflexology, in reducing preoperative anxiety and anxiety before other medical procedures.^{17,24,25}

Reflexology is a touch treatment method which is based on the theory that the entire body is represented in reflex points located on the soles of the feet (or the palms of the hands). A number of studies have examined the impact of reflexology treatments on indices of stress, anxiety and relaxation. 17,26,27

A handful of studies compared reflexology treatments with sham reflexology treatments (general foot massage without applying direct pressure to formal reflex points), to counteract the expected placebo effect.^{28,29} Such studies are important in order to isolate the treatment's placebo effect and highlight the specific effect, if any, of real reflexology.

Since elective LC is a very common operation, and due to the significance of preoperative anxiety in the context of potential postoperative complications and morbidity, we have examined the effect of reflexology as well as sham reflexology in parallel with SoC treatment which currently involves administration of anxiolytics, on this issue.

Methods

1. Type of study and study population

We conducted a single-blinded clinical intervention randomized controlled trial. Trial methods and results were reported according to the 2010 guidelines for Consolidated Standards of Reporting Trials (CONSORT) for non-pharmacologic interventions. The trial involved 300 patients awaiting an elective LC, who agreed to participate in the trial and were randomly allocated into three equal groups. Group 1 received the SoC treatment (anxiolytics) at the discretion of the anesthesiologist (n=100). Group 2 received reflexology treatment on top of SoC (n=101), and Group 3 received sham reflexology treatment in addition to SoC (n=99) (see Figure 1). The study was single-blinded because while patients in the study arms that involved reflexology did not know whether they were being treated with real reflexology or sham reflexology, and the treatment was described to them as medicinal foot massage rather than reflexology, the therapists, however, did know whether they were giving real or sham reflexology treatment.

Inclusion criteria: (1) Patients aged 18 years undergoing LC who consented to the study.

Exclusion criteria: (1) Patients with a history of obstructive sleep apnea; (2) Contraindication for benzodiazepines; (3) Hemodynamic instability; (4) Patients with feet ulcers; (5) Patients undergoing a LC together with another surgical procedure.

2. Study objective

The primary study objective was to examine the effectiveness of a combined treatment of reflexology on top of SoC in comparison to a combined treatment of sham reflexology on top of SoC and in comparison to SoC treatment alone in reducing preoperative anxiety in elective LC.

3. Sampling method and study procedure

The study was conducted at the Bnai Zion Medical Center in Haifa. Participants were recruited between July 2016 and October 2019.

Patients that agreed to be included in the study were randomly assigned to one of the three study groups using a designated software (randomization.com) (see Figure 1). Patients were asked to rate their level of anxiety and their level of comfort using the Visual Analog Scale (VAS) and VAS-A (Visual Analog Scale for Anxiety) questionnaire at the surgery department and in the HRA. Subsequently, patients were told whether they had been assigned to the intervention group involving foot massage – without specifying whether it would be real or sham reflexology – or to the control arm.

4. Therapeutic approach protocol

The study included three treatment groups:

A. SoC (group 1) included premedication about two hours before the operation with the anxiolytics Oxazepam and Diazepam, according to the anesthesiology department protocol and at the discretion of the anesthesiologist, regardless of the study arm. It should be clarified that in some cases the anesthesiologist decided not to administer anxiolytics, or the patient chose not to receive them. In cases where premedication was administered, the instructions were to administer 10mg of Diazepam to patients under the age of 65, and 10mg of Oxazepam to patients over 65. This protocol is supported by the study conducted by Pomara et al.²³ which found that older patients taking diazepam tend to suffer from side effects of memory and psychomotor performance impairments.

- B. Reflexology (group 2) intervention involved a 15-minute treatment in the induction room, provided by three reflexologists from the hospital staff. The reflexology protocol was developed through a Delphi method.³¹
- C. Sham reflexology (group 3) intervention were given by two complementary medicine practitioners with knowledge in touch therapy (shiatsu) and included 15 minutes of gentle, nonspecific foot massage. Similarly to the true reflexology protocol, the protocol for this treatment was also determined in a consensus-reaching process among a group of four experienced reflexologists.

5. Assessment tools

The level of anxiety was evaluated both before and after the treatments, using the VAS-A questionnaire for anxiety and the VAS scale for the level of comfort (rated from 0 – not comfortable at all, to 10 – very comfortable). VAS Comfort questionnaires were used in order to support the assessment of anxiety by VAS-A. The control group was assessed at the same time points. The questionnaire was given to the patient at the surgery department by a study coordinator. At the HRA questionnaires were given by the nursing staff before and after the intervention, shortly before the patient was transferred to the operating room.

Baseline assessment was carried out at the entrance to the HRA through a VAS-A

Paseline assessment was carried out at the entrance to the HRA through a VAS-A valid anxiety questionnaire for current anxiety level from 0—no anxiety, up to 10—maximum anxiety. ¹⁴ Similar to pain scale, it is common to divide the anxiety symptoms into categories; Low Anxiety (VAS-A≤4), Moderate to Severe Anxiety (VAS-A≥4), Severe Anxiety (VAS-A≥7).

7. Sample size calculation and statistical analysis

The calculation of the sample size was carried out using GPower software, which examines the sample size with reference to ANOVA variance analysis. The comparison between the three different groups, given a confidence level of 95%, power of 85% and an effect size that is considered medium according to Cohen's 0.25, alongside the definition of one unit of VAS as the low value for clinical significance³², required a sample size of at least 45 subjects per group. Due to the intention to use stratification to analyze the data of those with a VAS-A score above 4 (moderate-to-high anxiety), age, sex, as well as according to the administration of anxiolytics, approximately 100 subjects were recruited to each group. Since the result distribution was not normal, a variance test was conducted using Kruskal-Wallis' non-parametric test to compare the average change in preoperative anxiety in the induction room. Due to multiple comparisons (between 3 groups), the p-value in these tests was 0.014 in order to overcome the false discovery rate (FDR), and p<0.05 for the purpose of bilateral comparison.³³ Of note, both per-protocol and intention-to-treat analyses were planned, but since there was no patient cross-over, there was no need to differentiate between the analyses.

8. IRB approval

The study was approved by the local IRB (Helsinki Committee), approval no. BNZ-0041-09.

References

- 1. Sanders G, Kingsnorth AN (2007) Gallstones. BMJ 335:295–299.
- **2**. Greenberger N.J., Paumgartner G (2012). Chapter 311. Diseases of the Gallbladder and Bile Ducts.
- 3. ERAS Society Official Website, www.erassociety.org.

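### The primary test is unadjusted and no named analysis uses the ward VAS-A; covariate adjustment would add precision, most of it through the HRA-entry rating

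*Combined protocol and SAP*

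**What the plan says.** All references are to the combined protocol and SAP.

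- **Two pre-treatment ratings.** Section 3 has anxiety and comfort rated by "questionnaire at the surgery department and in the HRA". It continues: "Subsequently, patients were told whether they had been assigned to the intervention group involving foot massage". Both ratings therefore come before the patient knows the arm, although in the order of the text they follow randomisation.
- **Who collects them.** Section 5: "The questionnaire was given to the patient at the surgery department by a study coordinator". It adds: "At the HRA questionnaires were given by the nursing staff before and after the intervention". For the SoC arm: "The control group was assessed at the same time points".
- **Which one is baseline.** Section 5: "Baseline assessment was carried out at the entrance to the HRA through a VAS-A".
- **What is analysed.** Section 7 names a Kruskal-Wallis test "to compare the average change in preoperative anxiety in the induction room", giving non-normality as the reason. I read this as the difference between the HRA-entry and post-intervention ratings. No covariate is mentioned. Section 7 also intends stratified analyses by VAS-A above 4, age, sex and anxiolytic use, without saying which rating defines the VAS-A stratum.
- **Premedication.** Section 4 describes "premedication about two hours before the operation with the anxiolytics Oxazepam and Diazepam", given irrespective of arm. Whether the ward rating came before or after it is not stated.

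**The concern.** A single 0-10 self-rating is noisy. A change score subtracts the baseline with a fixed weight of one, which is generally not the most efficient use of it. A regression on baseline estimates that weight and can take in a second pre-treatment rating, whereas Kruskal-Wallis takes no covariates.

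The plan therefore uses the HRA-entry rating inefficiently and gives the ward rating no stated purpose. At stake is the precision of reflexology versus sham and reflexology versus SoC, and of the smaller comparisons within strata. Validity is not at stake: the planned contrast stands without any covariate.

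**Working it through.** **Inputs from the documents.** Three arms of 100, 101 and 99 (section 3). Section 7 gives effect size 0.25, 95% confidence, 85% power, 45 per group, 1 VAS unit as the lowest clinically significant value, and a threshold of 0.014 for the three-group tests. No SD and no correlation is given.

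**The plan's own figure.** With 45 per group, N = 135.
- One-way ANOVA: power at 45 per group is 73.2%, and 85% needs 60 per group. The stated 45 does not reproduce this way.
- Between-factor repeated-measures ANOVA, with 2 measurements and correlation 0.5 (both assumed): noncentrality = N·f²·m/(1+(m−1)ρ) = 135 × 0.0625 × 2/1.5 = 11.25. Power is 85.2% at 45 per group and 84.4% at 44, so 45 reproduces.

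This only makes 0.5 a convenient working value. The documents do not state it, and that variant tests the average of the two ratings, not the change.

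**Residual variance**, in units of the variance of one rating, with equal SDs assumed. Let r = corr(HRA entry, final), w = corr(ward, final) and v = corr(ward, HRA entry).
- Change score: 2(1−r)
- ANCOVA on HRA entry: 1−r²
- ANCOVA on HRA entry and ward: 1−(r²+w²−2rwv)/(1−v²)

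At r = 0.5:
- Change score: 2 × 0.5 = 1.00.
- HRA entry as covariate: 1−0.25 = 0.75, a 13.4% lower standard error than the change score.
- Ward added, all correlations 0.5: 1−(0.25+0.25−0.25)/0.75 = 0.667. The variance is a further 11.1% lower and the standard error 5.7% lower.
- Ward added, acting only through HRA entry (w = r·v = 0.25): 1−(0.25+0.0625−0.125)/0.75 = 0.75. There is no further gain.

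In the table, the last column runs from w = r·v to r = v = w.

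| r | Change | HRA entry | Both, r = v = w | Further variance cut from ward |
|---|---|---|---|---|
| 0.3 | 1.40 | 0.91 | 0.862 | 0 to 5.3% |
| 0.4 | 1.20 | 0.84 | 0.771 | 0 to 8.2% |
| 0.5 | 1.00 | 0.75 | 0.667 | 0 to 11.1% |
| 0.6 | 0.80 | 0.64 | 0.550 | 0 to 14.1% |
| 0.7 | 0.60 | 0.51 | 0.424 | 0 to 17.0% |
| 0.8 | 0.40 | 0.36 | 0.289 | 0 to 19.8% |

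For intermediate patterns (w, r, v), the ratio of two-covariate to one-covariate variance is 0.993 at (0.4, 0.7, 0.5), 0.980 at (0.5, 0.7, 0.6), 0.952 at (0.5, 0.6, 0.6) and 0.917 at (0.5, 0.6, 0.5). The further cuts are thus about 1% to 8%.

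**Cost of one degree of freedom.** With N = 300, residual df go from 296 to 295, and √(296/295) = 1.0017. The standard error rises by about 0.17%.

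**Power for one pairwise contrast.** The difference is 1 VAS unit, with 99 versus 101 patients, r = 0.5 and an assumed SD. Power = Φ(1/SE − z), where SE = SD·√(residual variance)·√(1/99+1/101).

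| SD | α | Change | + HRA entry | + ward |
|---|---|---|---|---|
| 2 | 0.05 | 94.2% | 98.3% | 98.3 to 99.1% |
| 2.5 | 0.05 | 80.7% | 90.4% | 90.4 to 93.4% |
| 3 | 0.05 | 65.4% | 77.7% | 77.7 to 82.3% |
| 2 | 0.014 | 86.0% | 94.8% | 94.8 to 96.9% |
| 2.5 | 0.014 | 64.5% | 79.1% | 79.1 to 84.3% |
| 3 | 0.014 | 46.0% | 60.4% | 60.4 to 66.6% |

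These figures are for comparisons of means. They indicate the relative gain and are not the power of the Kruskal-Wallis test itself.

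**The case against.** The strongest reply is that leaving out an optional covariate is not an error, and that the ward rating may add nothing. The HRA stay is 15 to 50 minutes (Background), so the HRA-entry and final ratings lie close together. The ward rating is earlier, in another place, taken by different staff, and possibly before premedication. If it predicts the final score only through HRA entry, its gain is zero. This stands as a bound. An exact zero is unlikely if each rating carries error: with assumed reliability of 0.7 to 0.9 and true-score correlation between adjacent ratings of 0.7 to 0.9, serial decay still gives a variance cut of 0.5% to 8%. Premedication could weaken the correlation but, being given irrespective of arm, does not bias the adjusted contrast.

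Two further replies stand in full. Every figure for the ward rating is an increment over an HRA-entry model that the plan does not contain, so the fix changes the primary model and its effect measure as well as adding a term. The text is also in the past tense, reports final group sizes and describes the outcome distribution, so adjustment chosen now may be post hoc.

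A reader might infer more than the documents support:
- **That every patient has a ward rating, or that few are missing.** Section 3 says only that patients were asked; completeness is not reported.
- **That the ward rating is certainly discarded.** Section 7 does not identify the rating behind the VAS-A stratum, although section 5 points to HRA entry.
- **That the sham contrast has the lowest power.** The arms are nearly equal, so this would need a smaller assumed effect, which the plan does not state.
- **That a proportional-odds model would give the same benefit.** Adding a covariate there changes the odds ratio being estimated, and the variance ratios above do not apply.

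**Conclusion.** The point holds as a precision gain forgone. Pre-treatment VAS-A ratings were collected, the named analysis adjusts for none of them, and the ward rating has no stated analytic use. At r = 0.5 with equal SDs, the HRA-entry covariate lowers residual variance from 1.00 to 0.75. The ward rating is expected to cut that by a further 0% to about 11%, or by up to about 17% if all correlations are 0.7. At an assumed SD of 2.5 and α = 0.05, the HRA-entry covariate adds about 10 points of power (80.7% to 90.4%) and the ward rating 0 to 3 points.

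It would be tempting to conclude that the ward rating is certain to tighten both primary contrasts at no cost. The documents do not support that: they give no correlation, the gain can be nil, and the change has the costs set out below. All magnitudes rest on assumed correlations, SDs and equal variances.

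**What to change.** Analyse final VAS-A by linear ANCOVA on arm, with HRA-entry VAS-A and ward VAS-A as covariates and robust standard errors, the latter because section 7 reports non-normality. Fill any missing ward rating by single mean imputation without regard to arm, so that no randomised patient is dropped on that account, and report how many were missing. Do the same for VAS comfort. Keep the Kruskal-Wallis result alongside. If outcomes have already been seen, label the ANCOVA a sensitivity analysis. State what the ward rating is for and which rating defines the VAS-A above 4 stratum.

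The data collection is already described, so the work is a short SAP paragraph and modest code. The costs are a different model and effect measure (an adjusted mean difference in VAS units, which can be set directly against the 1-unit threshold), one extra degree of freedom for the ward rating, and possibly little gain from that rating.

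### Does counting a VAS-A score of exactly 4 as both low and moderate-to-severe anxiety leave the stratified analysis undefined?

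*Combined protocol and SAP*

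**What the plan says.** Section 5 (Assessment tools) describes the VAS-A as a "valid anxiety questionnaire for current anxiety level from 0—no anxiety, up to 10—maximum anxiety". It then says that such scores are commonly grouped, and gives the groups as "Low Anxiety (VAS-A≤4), Moderate to Severe Anxiety (VAS-A≥4), Severe Anxiety (VAS-A≥7").

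Section 7 (Sample size calculation and statistical analysis) plans a separate look at "those with a VAS-A score above 4 (moderate-to-high anxiety"), together with age, sex and anxiolytic use. These four stratifiers are its reason for recruiting about 100 patients per group when the calculation asked for at least 45.

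On timing, section 3 has patients complete the "questionnaire at the surgery department and in the HRA", after which they learn whether they will receive foot massage. Section 5 adds: "At the HRA questionnaires were given by the nursing staff before and after the intervention". It also labels one rating: "Baseline assessment was carried out at the entrance to the HRA". Section 7 does not repeat which rating decides membership of the stratum.

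**The concern.** There are three apparent faults. A score of 4 satisfies both ≤4 and ≥4, so two of the classes in section 5 overlap. Under nearly the same label, section 5 includes a score of 4 and section 7 excludes it. And VAS-A was rated up to three times (surgery department, HRA before the intervention, HRA after it), yet section 7 does not say which rating places a patient above 4.

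The stratum is part of the stated reason for more than doubling recruitment. If its boundary or its time point were open, two analysts could form different subgroups from the same data, and a reader could not tell whether the choice was made before the results were seen.

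**Working it through.** The plan gives no figure on this point, so there is nothing to reproduce. The check is of the stated inequalities, followed by a bound on size.

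**Inputs.** From section 5: low ≤4, moderate to severe ≥4, severe ≥7, range 0 to 10. From section 7: stratum >4. From section 3: 300 patients, about 100 per group.

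**Step 1: apply each rule near the boundaries.**

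| Score | Low (≤4) | Moderate to severe (≥4) | Severe (≥7) | Section 7 stratum (>4) |
|---|---|---|---|---|
| 3.9 | yes | no | no | no |
| 4 | yes | yes | no | no |
| 4.1 | no | yes | no | yes |
| 7 | no | yes | yes | yes |

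The two sections differ only at exactly 4. Severe lying inside moderate to severe is nesting and not a conflict.

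**Step 2: count the classes.** In whole numbers there are 11 possible scores. As printed, ≤4 covers 5 and ≥4 covers 7; 5 + 7 = 12, one too many. With >4 the count is 5 + 6 = 11. In steps of 0.1 there are 101 possible scores: 41 + 61 = 102 as printed, and 41 + 60 = 101 with >4. So the section 7 rule and the low class in section 5 divide the scale with no gap or overlap. The ≥ in the middle class is the only statement out of line.

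**Step 3: see which rule is used.** The only analysis that needs a cut-off is the stratified one, and section 7 states that cut-off itself. No analysis is said to use the ≥4 class. The main comparison is a Kruskal-Wallis test of change in anxiety across the three groups and needs no cut-off.

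**Step 4: identify the rating.** The post-intervention score is not a sensible stratifier, because treatment can affect it. Of the two earlier ratings, only the one at HRA entry is called baseline, and the classes follow in the same paragraph. The surgery-department rating is nowhere called baseline.

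**Step 5: bound the size.** Patients affected = 300 × share scoring exactly 4. Neither that share nor the recording increment is in the documents, so every figure here rests on an assumption.

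- Even spread, steps of 0.1: 300 × 1/101 ≈ 3 (about 1 per group).
- Even spread, whole numbers: 300 × 1/11 ≈ 27 (about 9 per group).
- Assumed shares of 2% and 15%: 300 × 0.02 = 6 and 300 × 0.15 = 45 (2 and 15 per group).

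These figures count patients whose stratum would depend on the sign. They say nothing about a change in any result.

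**The case for a change.** The strongest case for acting concerns the rating, not the symbol. Premedication, where given, came roughly two hours ahead of surgery, and the Background puts the HRA stay at 15 to 50 minutes. The HRA-entry score therefore normally follows any anxiolytic. The documents do not say whether the surgery-department score came before or after it. The two ratings could place the same patient in different strata at scores well away from 4, and anxiolytic use is itself a stratifier. An analysis that helped to justify recruiting about 100 per group should be reproducible from the text.

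It is true that section 7 contains no explicit link to the HRA-entry score. But that score is the only one labelled baseline, and it is the one closest to the intervention. Section 3 also places both pre-treatment ratings before patients were told about their arm, so even the rival choice would form the subgroup on a pre-treatment measurement.

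On the symbol, the overlap is real as printed. However, the line introducing the paragraph appears twice in the text as read, once with a wrong first letter, so ≥ for > may be a reading artefact. Even if the source does print ≥, the entry is descriptive and the analysis section governs.

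**Conclusion.** The concern is correct on the text but calls for no change to the plan. The overlap at 4 is a clerical slip in a descriptive list, or an artefact of reading the PDF. Following section 7 as written gives a clean stratum of scores above 4, and correcting the sign in section 5 would change no result. The unnamed rating is a gap that section 5 lets an analyst fill sensibly with the HRA-entry baseline.

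The effect is confined to the stratified analysis; the primary comparison is untouched. The number of patients at exactly 4 cannot be derived from the documents, and the range of 3 to 45 of 300 is illustrative only.

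The document also describes a finished trial, with recruitment from July 2016 to October 2019. Writing in a particular sign or rating now, without knowing what was used, could misdescribe the analysis. Stating the cut-off and the rating actually used belongs to ordinary reporting of the subgroup result.

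This conclusion assumes that section 7 governs the analysis and that baseline carries the meaning section 5 gives it.

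### Does the absence of cross-over justify treating the planned intention-to-treat and per-protocol analyses as one?

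*Combined protocol and SAP*

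**What the plan says.** Section 7 states that "both per-protocol and intention-to-treat analyses were planned" and gives a single reason for reporting only one: "since there was no patient cross-over, there was no need to differentiate between the analyses". The visible text defines neither analysis set.

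Section 1 reports, in the past tense, 300 randomised patients, of whom 100 received standard of care (SoC), 101 reflexology plus SoC and 99 sham plus SoC. It refers to Figure 1, which is not reproduced in the text available here.

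The passages on timing are these:

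- Background describes the holding room area (HRA) as "a waiting room in which patients stay for 15-50 minutes before surgery".
- Section 5: "Baseline assessment was carried out at the entrance to the HRA through a VAS-A".
- Section 3, after the ratings: "Subsequently, patients were told whether they had been assigned to the intervention group involving foot massage".
- Section 4: reflexology "involved a 15-minute treatment in the induction room"; sham "included 15 minutes of gentle, nonspecific foot massage".
- Section 5, on the HRA: "questionnaires were given by the nursing staff before and after the intervention, shortly before the patient was transferred to the operating room".

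**The concern.** Cross-over is only one way in which treatment received can depart from treatment assigned. A patient called to theatre halfway through a massage has not crossed over. That patient stays in the ITT set but would leave a per-protocol set that required a complete session. The stated premise therefore does not deliver the stated conclusion.

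The timing makes such cases look foreseeable. If the whole sequence (baseline rating, disclosure of the arm, 15-minute session, second rating) must fit inside the HRA stay, a 15-minute stay leaves nothing for anything except the session.

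Two things would be at stake. A reader might take one result as showing both the effect of being assigned a massage and the effect of completing one. And because SoC has no session, exclusions for incomplete sessions could fall only on the massage arms, so a per-protocol contrast with SoC would set a selected group against an unselected one.

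**Working it through.** **The plan's own figure.** The only computed design figure is 45 per group (Section 7). A repeated-measures ANOVA on the between-groups factor reproduces it, with f = 0.25, alpha 0.05, two measurements and correlation 0.5 (the last two assumed): power is 85.2% at 45 per group. A one-way ANOVA would need 60. The present point does not depend on this; only f = 0.25 and the one-unit VAS threshold are used below, to obtain a standard deviation.

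**Do the documents show that the sets differed?** The patients described as having received each arm number 100 + 101 + 99 = 300, equal to the number randomised. No shortened or missed session is recorded. An anxiolytic that was not given or was declined is within discretionary SoC, so it is not a departure. A missing second rating, if there were any, would leave both sets alike and so would not separate them.

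**Time budget.** Let q be the minutes needed for both ratings and disclosure. Slack beyond the session runs from 15 − 15 = 0 to 50 − 15 = 35 minutes. A full session does not fit when the stay is below 15 + q. The documents give neither q nor a distribution of stays, so I assume q = 2, 5 or 10 and two stay distributions on 15-50 minutes:

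- Uniform: share too short = q/35.
- Symmetric triangular, peak 32.5: share too short = 2(q/35)².

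**Effect on the estimate.** Suppose a full session yields 1 VAS unit and stay length is unrelated to outcome. Per-protocol then shows 1.00, and the ITT estimate is lower by:

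- share × 1, if an incomplete session has no effect;
- share × 0.5, if it has half the effect;
- share × (mean minutes lost)/15, if benefit is proportional to minutes delivered. Mean minutes lost among short stays is q/2 (uniform) or q/3 (triangular), which gives q²/1050 and 2(q/35)² × q/45.

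| q | Stays | Share too short | Of 200 massage patients | Gap, no effect | Gap, half effect | Gap, proportional |
|---|---|---|---|---|---|---|
| 2 | uniform | 5.7% | 11 | 0.057 | 0.029 | 0.004 |
| 5 | uniform | 14.3% | 29 | 0.143 | 0.071 | 0.024 |
| 10 | uniform | 28.6% | 57 | 0.286 | 0.143 | 0.095 |
| 2 | triangular | 0.7% | 1 | 0.007 | 0.003 | 0.0003 |
| 5 | triangular | 4.1% | 8 | 0.041 | 0.020 | 0.005 |
| 10 | triangular | 16.3% | 33 | 0.163 | 0.082 | 0.036 |

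**Yardstick.** If one arm differs by 1 unit at f = 0.25, SD = (√2/3)/0.25 = 1.886. The standard error of one arm difference is 1.886 × √(1/100 + 1/101) = 0.266. The largest gap, 0.286, is about 1.1 standard errors. The largest proportional gap is 0.095/0.266 = 0.36. For q up to 5, the largest proportional gap is 0.024/0.266 = 0.09.

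**Which rows are credible?** The q = 10 rows assume slow ratings, yet Background recommends the VAS-A for its speed where contact time is short. The no-effect column treats a patient who lost a few of 15 minutes as untreated. The large figures need both assumptions.

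**Does the time budget apply at all?** Background calls the HRA a waiting room, whereas Section 4 puts reflexology in the induction room. That the session falls inside the 15-50 minutes is an inference. Both ratings around it are given at the HRA, and Section 7 places the anxiety change in the induction room, so the inference is reasonable but not stated. If session time lies outside the stay, the conflict disappears. Even inside it, the second rating comes before transfer to theatre, which is equally consistent with transfer waiting for the session to end.

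**The case for a change.** The best case for a change is that the logical fault is certain and the correction nearly free. To have received a treatment is not the same as to have completed 15 minutes of it, and Section 7 does not cite full delivery as its reason. If full delivery is the real reason, per-arm counts would show it; if sessions were cut short, the promised per-protocol analysis was never done.

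The logical part stands: absence of cross-over does not by itself make the sets coincide. The rest does not lead to a useful change. Per-arm flow may already be in Figure 1, so it cannot be called missing. A per-protocol comparison needs a criterion for a delivered session. The visible documents state none, and the text is written in retrospect, so any criterion set now would be post hoc. Excluding patients from the massage arms alone would also give up the protection of randomisation in the contrasts with SoC, in exchange for a secondary estimate. A further run that imputes missing second ratings would not bear on the sentence in question, and no missing ratings are recorded.

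**Conclusion.** The concern does not call for a change. Section 7 gives an incomplete reason for a choice that is itself sound, namely one analysis of patients in their allocated arm. The better reason is already in Section 1, where all 300 are described as having received their arm. An analyst would read the reported result as ITT, and would claim nothing separate about completed sessions unless session records supported it.

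The size cannot be determined from the documents. Across the assumed cases the gap between the analyses runs from 0.0003 to 0.286 VAS unit. With benefit proportional to minutes delivered it is at most 0.095, or 0.36 of a standard error. These figures assume that short stays occurred, that the session had to fit within them and that transfer did not wait; they also rest on the assumed q, stay distributions, one-unit effect and SD. The documents establish none of these. No bias in the main comparison is shown. Figure 1 or session records showing incomplete sessions would reopen the per-protocol question, but the ITT comparison would still stand.
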